Microbubbles can also act as pressure sensors due to the difference in compressibility between the bubble and the surrounding medium. Our group has proposed, patented and investigated a novel and innovative technique called subharmonic-aided pressure estimation (SHAPE). We have demonstrated that the subharmonic signal component from contrast microbubbles is an excellent indicator of the hydrostatic pressure variations. Changes in the first, second, and subharmonic amplitudes of five different ultrasound contrast agents were measured *in vitro* at static hydrostatic pressures from 0 to 186 mmHg (i.e., the range of human blood pressures). Over the pressure range studied the first and second harmonic amplitudes reduced approximately 2 dB for all contrast agents. Over the same pressure range, the subharmonic amplitudes decreased by 9-14 dB and excellent linear regressions were achieved between the subharmonic amplitude and the hydrostatic pressure variations ( $r^2 \geq 0.98$ ,  $p < 0.001$ ).

We implemented an initial, off-line version of the SHAPE algorithm on a commercial US scanner. SHAPE was realized on a phased array transducer (PA4-2) with a frequency range from 1.5-4.5 MHz and *in vivo* experiments were carried out in 4 canines with simultaneous measurements of pressure in the heart chambers performed with SHAPE and with a solid state pressure catheter (SPC-350; the reference standard).

Using SHAPE for IFP estimation in LABC requires a high frequency linear. As an *in vivo* proof-of-concept, 5 Sinclair swine with naturally occurring melanomas, were studied. Subharmonic signals were acquired (in triplicate) in tumors and surrounding tissues with the US scanner using an L14-5 probe. Definity was infused at a rate of 6.25 ml/min. RF data was

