acquired in pulse inversion grayscale mode at different transmit frequencies and acoustic power levels (6.7 and 10.0 MHz as well as -4, -8 and -12 dB). SHAPE results were compared to IFP measurements obtained with an invasive pressure monitor (Stryker, Berkshire, UK) as the reference standard. The difference between the subharmonics and the IFP in tumors and their surrounding tissues was most linear for 10 MHz transmission ( $r^2 \geq 0.67$ ;  $p < 0.05$ ; Fig 6). The slope from 3 out of 4 animals was similar to each other ( $-0.19 \pm 0.07$ ) and to the *in vitro* slope ( $-0.22$ ), while the last swine (i.e., swine 1) showed a large spread within the normal tissue IFP. These results provide proof-of-concept for the feasibility of using SHAPE as a noninvasive monitor of IFP.

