## **3. Specific Aims for the Human Clinical Trial.**

- 1) To evaluate the ability of 3D SHI and SHAPE to track changes in LABC angiogenesis and IFP, respectively, by studying women undergoing neoadjuvant chemotherapy before as well as with around 10% and 60% of the neoadjuvant chemotherapy treatment delivered and after

completion of the neoadjuvant chemotherapy treatment and comparing results to MRI and pathology.

- 2) Finally, as a secondary aim, to compare the 3D SHI depiction of breast cancer angiogenesis in humans to CD31, an immunohistochemical predictor of angiogenesis.

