#### *Data Assessments.*

The pre- and then post-contrast US imaging will be evaluated for each patient at all 4 time points in one reading as follows: grayscale, grayscale and PDI (baseline), and grayscale and 3D SHI. While this may introduced some bias from pre- to post-contrast results, we considered this the

more realistic approach to how US contrast may be used in clinical practice. Each case will be read independently by the 2 experienced co-investigators (more than 15 years of expertise in breast imaging) blinded to the contrast-enhanced MRI evaluations, to allow repeatability to be assessed. All US studies will be rated on a quasi-continuous scale from 0 to 100 ranging from “no change relative to pre-therapy” over “indeterminate” to “definite changes seen.” Using a quasi-continuous 100-point rating scale has an intuitive probabilistic interpretation and is known to improve the assessment of the capabilities of the imaging modes studied.

Moreover, the 3D SHAPE results (i.e., IFP estimates) will be compared to lesion size, tumor response, DFS and overall survival. Results will also be compared to MRI enhancement kinetics and imaging measurements of lesion size obtained before and after completion of the chemotherapy. Once surgery has been performed the following variables estrogen, progesterone and HER2 receptor presence or absences; presence or absence of hemorrhagic, necrotic, or other component of the lesion (and their location if present); histological margins; lesion size; TNM staging; histological lesion type; presence or absence of vascular invasion; histological and cytological grade; presence or absence of metastases; node staging; and percentage of the lesion that was invasive or *in situ* will be collected as part of the patient’s clinical care and correlated with the imaging results. Finally, the ability of 3D SHI to image angiogenesis (specifically fractional tumor vascularity) will be compared to specimens stained for an immunohistochemical predictor of angiogenesis, specifically a monoclonal antibody against the PECAM endothelial cell marker (anti-CD31; Dako Corporation, Carpinteria, CA). The PI has developed the necessary software for quantitative analysis of contrast enhanced US images and specimens

stained with CD31 using a histomorphometry system based on an SMZ-10A microscope (Nikon, Melville, NY) and ImagePro Plus software.

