*Statistical Analysis.* Our statistical analysis will address the primary objective of this study by answering two major questions:

1. Can *in vivo* 3D SHAPE monitor the effect of neoadjuvant chemotherapy on breast cancer IFP?
2. Can *in vivo* 3D SHI monitor the effect of neoadjuvant chemotherapy (i.e., responders/non-responders) on breast cancer?

The findings of SHI/SHAPE will be correlated to vascular morphology (i.e., tumor angiogenesis ascertained with CD31) and other pathological findings; including size, vascularity, presence or absence of receptors. For the pre and post-contrast enhanced comparisons, dichotomous parameters (e.g., responder/non-responder) and ranked data (less, iso, or more intense) will be analyzed with the McNemar test which measures significance of changes in related samples (pairwise comparisons) for each time point. For variables in which accurate numerical measurement is possible (e.g., IFP and vascularity), the techniques will be compared using repeated measures logistical regression and ANOVA.

To answer statistical question 2, the ability of the imaging tests to distinguish responders from non-responders will be compared using ROC analysis, while the incremental validity of combining imaging assessments will be analyzed using logistic regression and ROC analyses. The tests are fundamental grayscale US imaging, PDI, 3D SHI and contrast

enhanced MRI, while patient outcomes and pathology will provide the reference standards. A power analysis was performed using PASS 12 (NCSS, East Kaysville, UT) to estimate the number of cases required to produce clinically acceptable results. A sample size of 20 responders and 20 non-responders (i.e., approximately halfway between 20 and 50 subjects) achieve 80% power to detect a difference of 0.174 between a diagnostic test with an area under the ROC curve ( $A_z$ ) of 0.800 (the null hypothesis) and an actual  $A_z$  of 0.974 using a one sample, two-sided z-test with a significance level of 0.05. The ratio of the standard deviation of the responses in the two groups was assumed to be 1.00. All analyses will be performed with Stata 12.0 (Stata Corp., College Station, TX).

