### **6.3 Ultrasound Imaging**

The US examinations will be performed by a qualified sonographer. Procedures and equipment for this trial will be used in accordance with typical clinical procedures. All trial procedures will be conducted in accordance with Good Clinical Practice. For the ultrasound examination, the patient will be asked to lie in the supine position. Acoustic coupling gel will be applied to the breast area of interest. A baseline US grayscale scan will be used to identify the breast cancer seen by mammography (or another concomitant imaging mode such as US or MRI). Standard PDI of the tumor will also be performed. If the mass is too large to be completely imaged by the 4D10 L probe, the most vascular region seen on 2D PDI will be selected for the 3D SHI studies.

To perform the 3D SHI imaging, US software has been modified by GE Medical Systems on the clinical system, the Logiq 9 scanner, to permit acquisition of subharmonic data. All acoustic parameters have been verified and are all within the current standards of the machine, making the modified ultrasound system a non-significant risk device. US imaging will be performed at a transmit frequency of 5.8 MHz and the subharmonic obtained at 2.9 MHz. Using this setup, acoustic pressure amplitudes will all be below 1.5 MPa peak negative pressure, 2.5 MPa peak positive pressure ( $MI < 0.33$ ).

The contrast administration will be an intravenous infusion of 2 vials of Definity/50ml saline through the subjects' vascular port (established as part of their standard of care), with infusion rates of 4 to 10 ml/min (titrated to effect). Next, we will run a power optimization algorithm to establish the individualized acoustic parameter settings for the case (on the first imaging study only). We will use those parameters for all subsequent imaging studies to sweep the area of the LABC to acquire 3D, pulse inversion SHI grayscale volume data. The digital clips and radio frequency data obtained from each 3D SHI injection will be transferred to a PC for off-line analysis. The SHI images will be qualitatively analyzed as described above. This protocol will be followed for all the contrast studies for each subject (except for the power optimization algorithm, which will only be run once for each patient). All subjects will be closely monitored by a physician during and following the study.

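### Primary question 1 asks whether SHAPE monitors tumour interstitial fluid pressure, but nothing in the trial measures that pressure independently, so the question cannot be answered as posed

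*Combined protocol and SAP*

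**What the plan says.** The Statistical Analysis part of section 4 divides the primary objective into two questions. The first is whether "3D SHAPE monitor the effect of neoadjuvant chemotherapy on breast cancer IFP". The hypothesis in sections 2 and 7.2.1 says that subharmonic signals can measure breast cancer IFP noninvasively.

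The planned comparisons are these:

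- Specific aim 1 (section 3) follows patients until "completion of the neoadjuvant chemotherapy treatment and comparing results to MRI and pathology".
- Data Assessments (section 4) says that "the 3D SHAPE results (i.e., IFP estimates) will be compared to lesion size, tumor response, DFS and overall survival", and adds MRI enhancement kinetics, lesion size on imaging and a list of surgical pathology variables.
- For the ROC analyses (section 4 and section 7.2.2), "patient outcomes and pathology will provide the reference standards". SHAPE enters there through logistic regression, as a quantitative parameter added to the ultrasound modes.
- Section 4 also groups IFP with the variables that can be measured accurately as numbers, to be analysed by repeated-measures regression and ANOVA.

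An independent tumour pressure reading appears only in the animal work in the Introduction, where "SHAPE results were compared to IFP measurements obtained with an invasive pressure monitor". On the acquisition in this trial, section 6.3 states: "US imaging will be performed at a transmit frequency of 5.8 MHz and the subharmonic obtained at 2.9 MHz".

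**The concern.** A study that asks whether an instrument tracks a quantity needs a second measurement of that quantity, or a calibration that carries over from elsewhere. The patients have no second measurement. The calibration in the documents comes from a different probe, different frequencies and a different tumour.

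There is a further difficulty. SHI reads more subharmonic signal as more vascularity, while SHAPE reads less subharmonic signal as higher pressure. The protocol describes one contrast acquisition per visit and no separate one for SHAPE. A change in perfused vessels during chemotherapy could therefore appear in the SHAPE output as a change in pressure.

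At stake is the conclusion on one of the two primary questions. Under the plan as written, a change in SHAPE would be reported as an effect of chemotherapy on IFP, and H1 would be taken as supported, without evidence that pressure was what changed.

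**Working it through.** **The plan's own figure.** The only power statement (80%, area under the curve 0.800 against 0.974, 20 responders and 20 non-responders) belongs to question 2. With a binormal variance and no covariance term, the standard errors are 0.0775 under the null and 0.0264 under the alternative. Power = Φ((0.174 − 1.96 × 0.0775)/0.0264) ≈ 0.80, so that variance formula reproduces it. It has no bearing on question 1, which has no power or precision statement.

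**Step 1: is there a pressure reference?** Taking the comparators in turn: lesion size, tumour response, disease-free survival, overall survival, MRI kinetics, MRI lesion size, surgical pathology and CD31. None is a pressure. SHAPE could agree perfectly with response and still not show that IFP was tracked.

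**Step 2: does outside calibration carry over?** The Introduction gives three sources:

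- In vitro: five agents over 0-186 mmHg, where "the subharmonic amplitudes decreased by 9-14 dB".
- Canine: heart-chamber pressures with a PA4-2 phased array. This is not tumour IFP.
- Swine melanoma: an L14-5 probe at 6.7 and 10 MHz. The relation "was most linear for 10 MHz transmission" (r² ≥ 0.67), and slopes were similar in 3 of 4 animals.

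This trial uses the 4D10L at 5.8 MHz. The documents give no calibration for that setting.

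**Step 3: do the documents' slopes agree?**

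- In vitro range: 9/186 = 0.048 and 14/186 = 0.075 dB/mmHg.
- Swine work: 0.19 (± 0.07) in vivo and 0.22 in vitro, in absolute value. Units are not printed; dB/mmHg is assumed.
- Ratios: 0.19/0.075 = 2.5 and 0.22/0.048 ≈ 4.5.
- A 1 dB change would read as 1/0.22 = 4.5 to 1/0.19 = 5.3 mmHg on one set, and 186/14 = 13.3 to 186/9 = 20.7 mmHg on the other.

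**Step 4: an illustrative treatment effect.** The Introduction cites a mean breast cancer IFP of 29 mmHg and, from a different study, a 36% fall with paclitaxel. 0.36 × 29 = 10.4 mmHg. In signal this is 10.4 × 0.19 = 2.0 dB to 10.4 × 0.22 = 2.3 dB, or 0.5 to 0.8 dB at 0.048-0.075.

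**Step 5: how large could the vessel effect be?** Assume received subharmonic power is proportional to the number of perfused bubbles, the signal is averaged over a fixed region, and true IFP is unchanged. Apparent pressure rise = −10 log10(1 − loss)/slope.

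| Perfused vessel loss | Signal fall | Slopes 0.22 to 0.19 | Swine range 0.26 to 0.12 | Slopes 0.075 to 0.048 |
|---|---|---|---|---|
| 25% | 1.25 dB | 5.7 to 6.6 mmHg | 4.8 to 10.4 mmHg | 17 to 26 mmHg |
| 50% | 3.01 dB | 13.7 to 15.8 mmHg | 11.6 to 25.1 mmHg | 40 to 62 mmHg |

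Under the same assumptions, a loss of 37-41% (slopes 0.19-0.22) or 11-17% (slopes 0.048-0.075) would cancel the signal of a true 10.4 mmHg fall.

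**The case against.** The strongest reply is that this is an open-label first-in-humans study. Its aim is to track changes, its SHAPE output is already called an estimate, and nobody would ask for invasive pressure readings in these patients. That is a good reason not to add a measurement. It does not rescue question 1 or H1, which are worded as monitoring and measuring IFP.

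Other points on that side stand, and they limit the second half of the concern:

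- A reader might infer that vessel loss will be read as rising pressure. No passage says that amplitude falls with vessel loss, and the off-line SHAPE algorithm is not described. It may use only contrast-filled voxels or a tissue reference; the swine work considered tumour and surrounding tissue together.
- A reader might infer that the artefact must exceed the treatment effect. It need not: a 25% loss at slope 0.22 gives 5.7 mmHg, about 0.55 of 10.4 mmHg.
- A reader might infer that the Introduction expects IFP to fall in responders. It reports that one agent lowered mean IFP and the other did not, and that clinical outcomes were unavailable.
- A reader might infer that SHI and SHAPE are never analysed together. Section 7.2.2 puts both into one response model, and section 4 correlates both with CD31. The first predicts response and does not separate pressure from vascularity. The second uses specimens, so it cannot correct within-patient change over four visits.
- The per-patient acoustic power optimisation cites a paper on SHAPE, so the settings are not arbitrary. The documents do not present it as a conversion from dB to mmHg.

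**Conclusion.** Question 1 and the SHAPE part of H1 are wrong as written. This rests on the documents alone and needs no assumption: no comparator is a pressure, and the one tumour validation used a different probe and different frequencies. The disagreement between slopes, about 2.5- to 4.5-fold, adds that any conversion to mmHg is unsettled. It depends on the unprinted swine units being dB/mmHg.

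The shared-signal problem is a possibility that the plan does not exclude, not a demonstrated bias. Its illustrative size, roughly +6 to +16 mmHg for 25-50% vessel loss at slopes 0.19-0.22 against about 10 mmHg, depends on proportional power, the assumed units, region averaging and vessel losses that the documents do not give. The documents do not support a claim that the sign of the SHAPE result will be reversed. Nor do they show that SHAPE fails to measure IFP; the trial simply cannot tell.

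**What to change.** 1. Restate question 1 and the SHAPE part of H1 (sections 2, 4 and 7.2.1): does the SHAPE signal, in dB, change during chemotherapy, and does that change differ between responders and non-responders?
2. Report dB as the main result. Label any mmHg conversion as unvalidated and name the slope used.
3. State that the trial does not validate IFP measurement.
4. Describe the SHAPE processing: the region, the voxels and any reference tissue.
5. As sensitivity analyses only, beside the unadjusted result, show SHAPE change over contrast-filled voxels in the stored RF data, and SHAPE change with same-visit SHI fractional vascularity in the model. Say plainly that this covariate is measured after treatment starts, comes from the same echoes and may remove genuine pressure change. A tumour-minus-surrounding-tissue difference would not cancel vessel loss confined to the tumour, so it should not be offered as the remedy.

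The cost is a more modest claim, some rewording and a little extra off-line analysis. No new patient procedure is needed.

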### *Patient Enrollment*

At TJU, [name] (the medical oncologist on this project) and her colleagues treat more than 500 women with breast cancer each year out of which 1-2 women/week will be treated with neoadjuvant chemotherapy. We expect to enroll between 20 and 50 subjects undergoing neoadjuvant chemotherapy (i.e., 10 – 25 women/year) in this *first-in-humans* project who will be studied with contrast US (SHI and SHAPE) before as well as with around 10 % and 60% of the neoadjuvant chemotherapy treatment delivered and after completion of the last chemotherapy treatment. Thus, a total of some 144 contrast studies will be performed in this project (range: 80 – 200). The patients studied in this project will be women over the age of 21, who will receive an MRI as part of their standard of care (before and after completion of the chemotherapy). The MRI results together with pathology findings will be compared to the 3D SHI and SHAPE studies as a means for treatment monitoring.

Given that these women have been diagnosed with breast cancer, they are usually very motivated to participate in research studies that include additional monitoring and, therefore, we do not expect recruitment to be an issue. The patient population of this project will reflect the population demographics found at major American urban academic health centers. The overall hospital demographics for TJU include 60 % Caucasian, 16 % African American, 13 % Hispanic, 5 % Asian, 1 % Other, and 5 % unknown patients. Breast cancer in males accounts for only about 1% of cases at TJU and, thus, will not be included in the patient population.

The inclusion criteria for this trial are as follows:

- Females
- Be diagnosed with T1 or greater LABC, any N and M0.

- Be scheduled for neoadjuvant chemotherapy
- Be at least 21 years of age.
- Be medically stable.
- If a female of child-bearing potential, must have a negative pregnancy test.
- Have signed Informed Consent to participate in the study.

The exclusion criteria are:

- Males
- Females who are pregnant or nursing.
- Patients with other primary cancers requiring systemic treatment.
- Patients with any metastatic disease.
- Patients undergoing neoadjuvant endocrine therapy.
- Patients with known hypersensitivity or allergy to any component of Definity.
- Patients with cardiac shunts or congenital heart defects.
- Patients with unstable cardiopulmonary conditions or respiratory distress syndrome.

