## 6.7 End-of-Treatment and End-of-Trial Evaluations

### 6.7.1 Discontinuation of Subjects

Subjects will be free to discontinue trial participation at any time. The investigator will also discontinue any subject from the trial if, in the investigator's opinion, it is not safe for the subject to continue. The date the subject is withdrawn from a treatment and/or from the trial and the reason for discontinuation will be recorded on the CRF.

Trial participation will be considered completed if the subject has met all of the trial requirements that is to participate in 4 US contrast studies during the duration of their clinical cancer treatment.

If a subject's participation in the trial is interrupted for any reason (e.g., because of an AE or if the subject is lost to follow-up) and the subject has met the criteria described above for completing the trial, the subject's trial participation will be considered completed. If a subject's trial participation is interrupted

for any reason by the subject's or investigator's choice and the subject has not met all of the criteria listed above, then the subject will be considered a discontinued subject.

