#### **7.2.2 Analysis of Results**

For the pre and post-contrast enhanced comparisons, dichotomous parameters (e.g., responder/non-responder) and ranked data (less, iso, or more intense) will be analyzed with the McNemar test which

measures significance of changes in related samples (pairwise comparisons). For variables in which accurate numerical measurement is possible (e.g., IFP and vascularity), the techniques will be compared using logistical regression and an ANOVA.

The ability of the imaging tests to distinguish responders from non-responders will be compared using ROC analysis, while the incremental validity of imaging assessments will be analyzed using logistic regression and ROC analyses. The tests are fundamental grayscale US imaging, PDI, 3D SHI and contrast enhanced MRI, while patient outcomes and pathology will provide the reference standards. All studies will be rated on a quasi-continuous scale from 0 to 100, since this has an intuitive probabilistic interpretation and improves the assessment of the characterization capabilities of the imaging modalities compared to using a coarser 6-point scale. Logistical regression techniques will be used to combine the 3 US imaging modes and MRI as well as to incorporate the quantitative parameters (i.e., SHAPE IFP estimates) into the US evaluation before repeating the ROC analysis. This will allow all possible combinations to be compared to one another (e.g., MRI versus all the US modes combined or MRI and grayscale US versus MRI and grayscale US and SHI, etc.). Differences between ROC curves will be tested by computing Mann-Whitney statistics.

All histopathological variables will be compared to imaging judgments of vascularity for the different modalities. When both sets of variables are nominal, chi-square tests will be conducted. When both types of variables are ordinal or continuous, correlations will be calculated. When one type of variable is nominal and one continuous non-parametric rank order tests such as Mann-Whitney U-tests or Kruskal-Wallis tests will be performed. Inter-observer variability will also be determined by calculating the intraclass correlation coefficient.

Comparisons of subject outcomes (i.e., responders vs. non-responders) established by monitoring the treatment with the different imaging modalities will be conducted with Cox Survival analysis (against

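### The two analysis sections disagree on whether continuous IFP is analysed as a repeated measure, and both name logistic regression for it without stating a change-over-treatment contrast for primary question 1

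*Combined protocol and SAP*

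**What the plan says.** Section 4 (Research Strategy), paragraph Statistical Analysis, splits the primary objective into two questions. The first is "Can *in vivo* 3D SHAPE monitor the effect of neoadjuvant chemotherapy on breast cancer IFP". The second concerns 3D SHI and responder status.

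Only the second has a labelled method: "To answer statistical question 2, the ability of the imaging tests to distinguish responders from non-responders will be compared using ROC analysis". The single power calculation belongs to it as well.

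The one sentence in Section 4 that gives a method for IFP as a measured quantity opens "For variables in which accurate numerical measurement is possible (e.g., IFP and vascularity" and then says "the techniques will be compared using repeated measures logistical regression and ANOVA". Section 7.2.2 (Analysis of Results) repeats the sentence, but ends it "the techniques will be compared using logistical regression and an ANOVA".

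Two design facts matter here. Section 6.7.1 defines completion as having to "participate in 4 US contrast studies during the duration of their clinical cancer treatment". The Patient Enrollment paragraph says "We expect to enroll between 20 and 50 subjects undergoing neoadjuvant chemotherapy".

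On ROC analysis, both sections give the same list: "The tests are fundamental grayscale US imaging, PDI, 3D SHI and contrast" enhanced MRI. SHAPE is not on it. Section 7.2.2 then adds that logistic regression will combine the imaging modes and bring in the SHAPE IFP estimates before the ROC analysis is run again.

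**The concern.** IFP from SHAPE is continuous and is measured four times in each woman. Measured against that, the stated method has four faults.

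- **Outcome type.** Logistic regression models a categorical outcome. It cannot have continuous IFP as its outcome, and adding repeated measures to its name does not change this.
- **Disagreement.** Section 4 carries the words repeated measures and Section 7.2.2 does not. Section 7.2.2 is the formal analysis section, so an analyst following it literally could fit an ANOVA with no patient term.
- **Comparison.** The sentence compares techniques. Among the techniques in the plan, only SHAPE estimates IFP, so for IFP there is no second technique to compare.
- **Contrast.** Question 1 is about change under treatment. No passage states a visit effect, a change from the pre-therapy scan, or a difference in change between responders and non-responders.

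In a study of 20 to 50 women, the choice between the two texts could decide whether a real fall in IFP is detected.

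**Working it through.** **1. The plan's own figure.** It is 80% power for Az 0.800 versus 0.974 with 20 responders and 20 non-responders, two-sided 0.05, SD ratio 1.00. With the binormal variance, SE0 = 0.0775 and SE1 = 0.0264, so power = Φ((0.174 − 1.96 × 0.0775)/0.0264) = Φ(0.84) ≈ 0.80. The figure reproduces, but it concerns question 2. There is no corresponding figure for question 1.

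**2. Inputs for question 1.** From the documents: 4 scans per patient; 20 to 50 patients, with 40 used in the power calculation. The documents give no SD for IFP, no between-visit correlation ρ and no target change. Assumptions: equal correlation between visits, ρ = 0.3, 0.5 or 0.7; a linear fall totalling 0.5 SD over the four scans; α = 0.05.

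**3. Standard error of a change over time.** For n patients with variance σ², the true variance of the mean difference between two visits is 2σ²(1 − ρ)/n. An analysis that ignores the pairing uses 2σ²/n. The ratio of standard errors is 1/√(1 − ρ):
- ρ = 0.3: 1/√0.7 = 1.20
- ρ = 0.5: 1/√0.5 = 1.41
- ρ = 0.7: 1/√0.3 = 1.83

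**4. Effect on the test.** Simulation, 20,000 replicates per scenario, comparing one-way ANOVA without a patient term with repeated-measures (RM) ANOVA. Each cell gives the results for ρ = 0.3 / 0.5 / 0.7.

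| N | Quantity | No patient term | RM ANOVA |
|---|---|---|---|
| 40 | Type I error | 0.010 / 0.002 / <0.001 | 0.047 / 0.050 / 0.052 |
| 40 | Power | 0.42 / 0.36 / 0.28 | 0.63 / 0.80 / 0.96 |
| 20 | Power | 0.17 / 0.11 / 0.06 | 0.33 / 0.46 / 0.69 |
| 50 | Power | 0.53 / 0.51 / 0.46 | 0.74 / 0.88 / 0.99 |

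For a change over time, ignoring the correlation is conservative. The loss is power, not false positives.

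**5. A responder comparison that pooled all scans.** The plan does not state this analysis, so the figures are conditional. A patient's mean over four scans has variance σ²(1 + 3ρ)/4, where independence would give σ²/4. Type I error is then 2(1 − Φ(1.96/√(1 + 3ρ))):
- ρ = 0.3: √1.9 = 1.378, giving 0.155
- ρ = 0.5: √2.5 = 1.581, giving 0.215
- ρ = 0.7: √3.1 = 1.761, giving 0.266

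**The case against.** The best defence is that Section 4 already names a usable method. Its modifier naturally extends to ANOVA, and repeated-measures ANOVA handles a continuous measure over four scans; step 4 shows that it holds its level. This stands. A reader might infer that question 1 cannot be answered by any method named in the plan, and the documents do not support that.

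Other parts of the defence also stand:

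- Section 7.2.2 does not say ordinary ANOVA, and it does not say that scans are treated as independent. Both are inferences from a missing modifier.
- A reader might infer that SHAPE is left out of the ROC work. It is not: Section 7.2.2 enters the IFP estimates, in combination with the imaging modes, in a second ROC analysis. Only SHAPE on its own is missing.
- A reader might infer that the plan carries a 15% to 27% false-positive rate. Those figures need a pooled responder test that the plan never states. Elsewhere it works by time point, for the McNemar tests and the Cox analysis.
- A reader might call repeated-measures logistic regression impossible because response is one value per patient. Section 4 lists responder status among the parameters tested at each time point, so response as called by imaging may vary by visit. Logistic regression with IFP as a predictor of response is legitimate.
- The comparison of techniques is not empty for vascularity, which Section 7.2.2 considers in both baseline PDI and contrast-enhanced mode.

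None of this removes the disagreement between the sections, the mismatch between logistic regression and a continuous outcome, or the missing contrast for question 1.

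**Conclusion.** The point holds in limited form. The sentence governing IFP is wrong where it assigns logistic regression to a continuous outcome. It appears in two versions that differ on the feature that matters most for four scans per patient. On neither version does it state the change-over-treatment comparison that question 1 needs.

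The size depends on which version is followed. Under repeated-measures ANOVA there is no calibration problem in the simulated setting. Under the literal Section 7.2.2 text, the standard error of change is 1.20 to 1.83 times too large, and with 40 patients power falls by roughly 0.2 to 0.7 in absolute terms (0.63 − 0.42 = 0.21 at ρ = 0.3; 0.96 − 0.28 = 0.68 at ρ = 0.7).

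The standard-error ratios rest on the assumed correlations; the power figures also rest on the assumed 0.5 SD fall. The disagreement and the outcome mismatch rest on the text alone. Because one of the two primary questions is affected, the wording should be settled before analysis.

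**What to change.** Put the same text in Section 4 and Section 7.2.2:

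- **Model.** Analyse the SHAPE IFP estimate, and separately fractional vascularity, in a linear mixed model with all four visits as outcomes, a patient random effect, and fixed effects for visit, response and visit-by-response. Repeated-measures ANOVA with the same terms is an acceptable alternative. Keep the pre-therapy scan as an outcome, not as a covariate, so that change from it is estimated directly.
- **Contrasts.** State two: change from pre-therapy at each later visit, and the visit-by-response difference. Say whether the first is averaged over the response groups.
- **Techniques.** Where vascularity is measured by more than one technique (PDI and SHI), add technique as a within-patient factor so that the planned comparison is kept.
- **Logistic regression.** Keep it only for the responder outcome, with IFP as a predictor.
- **ROC.** Add SHAPE alone to the listed tests, beside its existing use in combination.

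Use the protocol's own IFP estimate as the outcome. A tumour-minus-surrounding-tissue difference is described only in the swine work, and the human procedure does not specify it.

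The cost is SAP wording and a little more analysis. No new data are needed.
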